#### *Initial Screening*

Three study forms will be completed during the initial screening session, which includes 1) the informed consent form, 2) the Knee Injury History Form and 3) the Western Ontario and McMaster Universities Osteoarthritis Index (WOMAC).

#### **Informed Consent Form**

Written and verbal consent will be obtained before any additional questionnaires are completed or any study data is collected. The Principal Investigator, Study Coordinator or Research Assistant will provide the potential study participant with the consent form and explain each part of the consent form with the potential study participant. The potential study participant will be allowed to ask any additional questions about the study. Upon providing verbal and written consent, a copy will be made of the signed consent form. One copy will remain in the participant's binder and the other copy will be given to the study participant to keep for their records.

## **Knee Injury History Form**

The Knee Injury History Form first asks a series of yes or no questions in order to determine if the study participant meets the specific inclusion and exclusion criteria for the study. The next set of questions asks about previous knee osteoarthritis treatments such as intraarticular injections and physical therapy, and asks for detailed information regarding each type of treatment. The last section of Knee Injury History Form asks a series of questions about types of medication use that is taken specifically for pain as well as any other medications taken. Participants are asked to complete a medication log which details the type of medication, as well as the dose, frequency and time of day the medication is taken. Data from the medication use and medication logs will be used as potential statistical covariates.

## **WOMAC**

The WOMAC will be used to assess self-reported disability. The WOMAC consists of 24 items divided into three subscales which individually assess pain, stiffness and physical function in individuals with knee osteoarthritis. The pain subscale consists of 5 items and assesses the magnitude of knee pain during walking, using stairs, in bed, sitting or lying, and standing. The stiffness subscale consists of 2 items and assesses the magnitude of stiffness after first waking in the morning and later in the day. The physical function consists of 17 items and asks about the magnitude of difficulty when ascending and descending stairs, rising from sitting, standing, bending, walking, getting in / out of a car, shopping, putting on and taking off socks, rising from bed, lying in bed, getting in and out of the bath, sitting, getting on and off the toilet, completing heavy household duties, and completing light household duties. Each item is presented in a 5 point Likert-type format and uses the following descriptors for possible answer choices none, mild moderate, severe, and extreme. Each descriptor corresponds to an ordinal scale of 0-4. The scores are summed for the items in each subscale, with possible ranges as follows: pain=0-20, stiffness=0-8, physical function=0-68. Higher scores on the WOMAC indicate greater amounts of pain, stiffness, and functional limitations.

## *Baseline Assessment*

Five questionnaires will be completed during the baseline assessment, which occurs within 7 days prior to the initiation of the intervention and includes 1) the Physical Activity Scale for the Elderly (PASE), 2) Self-Efficacy for Physical Activity (SEPA), 3) the Short Form 12 (SF-12), 4) the Charlson Morbidity Index, and 5) Visual Analog Scales (VAS) to determine the likelihood to continue current level of physical activity, current level of knee pain, and tolerability of walking.

## **PASE**

The PASE measures the level of physical activity in individuals age 65 and older. The PASE is comprised of measures of self-reported occupational, household, and leisure activities during a one-week period. The PASE consists of 12 items which determine the frequency and duration of leisure activities (e.g., sports, jogging, swimming, strengthening and endurance exercise), household activities, and work-related activities. Items are scored differently depending upon the type of activity that is being quantified. Participation in leisure-time and strengthening activities are scored as never, seldom (1-2 days per week), sometimes (3-4 days per week), and often (5-7 days per week). Duration of these activities is scored as less than 1 hour, 1-2 hours, 2-4 hours and more than 4 hours. Household and work related activities are scored as yes or no. In work related activities, paid or unpaid work is scored in total hours per week. The total PASE score is computed by multiplying either the time spent in each activity (hours per week) or participation (i.e., yes/no) in an activity, by empirically derived item weights and then summing overall activities. The overall PASE score ranges from 0 to 400 or more, where higher scores indicate greater levels of physical activity.

## **SEPA**

The SEPA questionnaire assesses how confident individuals are in their ability to be physically active in a variety of situations, including when they are: tired, in a bad mood, do not feel they have enough time, on vacation, when it is snowing or raining. The SEPA consists of 5 items and each item is presented in a 5 point Likert-type format. Each item uses the following descriptors for each item: not at all confident, slightly

confident, moderately confident, very confident, and extremely confident. These correspond to an ordinal scale of 1-5. The point value from each question is summed for a total score. Higher scores indicated higher levels of confidence in the ability to be physically active.

### **SF-12**

The SF-12 is used to assess functional health and well-being from the patient's point of view. The SF-12 consists of 12 items which assess all 8 domains of health, including: physical functioning, role-physical, bodily pain, general health, vitality, social functioning role-emotional and mental health. Each item is presented in either a 3 or 5 point Likert-type format. Pre-coded values are assigned to each possible answer for each item. Raw scores from each item are totaled, and raw scores can be transformed into 0-100 scale scores. Higher scores on the SF-12 indicate better general health perceptions.

### **Charlson Comorbidity Index**

The Charlson Comorbidity Index is a method of categorizing comorbidities of patients based on the International Classification of Diseases (ICD) diagnosis codes found in administrative data. Each comorbidity category has an associated weight, based on the adjusted risk of mortality or resource use, and the sum of all the weights results in a single comorbidity score for a patient. A score of zero indicates that no comorbidities were found. The higher the score, the more likely the predicted outcome will result in mortality or higher resource use.

### **VAS to determine tolerability of walking, current level of knee pain, and likelihood to continue current level of physical activity**

The VAS for tolerability of walking will be completed immediately upon completion of the first trial of the 20-meter walk test. Participants are asked to make a vertical line on a 100mm solid line to indicate how tolerable they feel walking was during the task just completed. The VAS ranges from "Not at all Tolerable" on the left to "Extremely Tolerable" on the right. VAS scores closer to 100, or marks closer to the rightward end, indicate a greater tolerability of walking. The VAS for the current level of knee pain asks participants to make a vertical line on a 100mm solid line to indicate how much pain they currently have in their knee. The VAS ranges from "No Pain" on the left to "Worst Pain Imaginable" on the right. VAS scores closer to 100, or marks closer to the rightward end, indicate a greater amount of knee pain. The VAS for the likelihood to continue their current level of physical activity asks participants to make a vertical line on a 100mm solid line to indicate how likely they are to continue their current level of physical activity. The VAS ranges from "Not at all Likely" on the left to "Extremely Likely" on the right. VAS scores closer to 100, or marks closer to the rightward end, indicate a greater likelihood of continuing the current level of physical activity.

### *Duration of the Intervention*

During each week of the intervention, participants will be asked to complete a daily medication log and will be given a VAS in order to assess 1) tolerability of the intervention, 2) satisfaction with the intervention, 3) likelihood to retain following week's appointments.

### **Medication Log**

For each day of the week participants will be asked to write down each medication taken. Participants are asked to include the name of the medication, the dose of the medication, the frequency of use, and the time of day the medication is taken. Medication use throughout the study will be used as a statistical covariate if necessary.

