### **3.j Concomitant Medications**

All medications that the each patient is currently prescribed or using as well as been prescribed and has taken in during the previous 4 weeks will be collected at the baseline visit. We will also collect data about the medications on a daily basis using a medication log. We will restrict certain medications for the entirety of the study, at certain time points during the study and for a period of time before the screening visit.

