### Medication Restrictions

*Corticosteroid injections* into the knee or any lower extremity joint will be restricted for 14 days prior to the screening visit (based on the drug half-life) and throughout the entirety of the study period including the 8-week follow-up test. We will collect information about when the latest corticosteroid injection occurred for each participant at the prior to screening in order to determine when each participant can attend the screening visit.

*Hyaluronic acid injections* into the knee or any lower extremity joint will be restricted for 14 days prior to the screening visit (based on the drug half-life) and throughout the entirety of the study period including the 8-week follow-up test. We will collect information about when the latest hyaluronic acid injection occurred for each participant at the prior to screening in order to determine when each participant can attend the screening visit.

*Prescription Depressants* (Examples: opiates and opioids, barbiturates, tranquilizers and benzodiazepines) will be restricted 4-weeks prior to screening and throughout the study period as these medications may affect the neuromuscular function.

*Prescription Stimulants* (Example: amphetamines) will be restricted 4-weeks prior to screening and throughout the study period as these medications may affect the neuromuscular function.

*Non-steroidal anti-inflammatory drugs (NSAIDs)* will be restricted 24 hours prior to screening or follow-up testing sessions. We will track NSAIDs and instruct patients not to change their NSAIDs usage during the 8-weeks of the study.

*Acetaminophen* will be restricted 24 hours prior to screening or follow-up testing sessions. We will track Acetaminophen and instruct patients not to change their Acetaminophen usage during the 8-weeks of the study.

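### The plan allows medication use recorded after randomisation to be entered as a covariate at discretion, although TENS may itself affect that use

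*Combined protocol and SAP*

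**What the plan says.** Section 3.n.1, under Medication Log, states: "Medication use throughout the study will be used as a statistical covariate if necessary". The paragraph before it, Duration of the Intervention, sets the timing: "During each week of the intervention, participants will be asked to complete a daily medication log". Section 3.j also describes a daily log and separately provides for baseline data. Current medications are recorded, together with what the patient "has taken in during the previous 4 weeks will be collected at the baseline visit".

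The Knee Injury History Form text in 3.n.1 adds: "Data from the medication use and medication logs will be used as potential statistical covariates". That form is listed under Initial Screening.

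Section 3.j, Medication Restrictions, limits drug use during the study. For NSAIDs: "We will track NSAIDs and instruct patients not to change their NSAIDs usage during the 8-weeks of the study". The same instruction is given for acetaminophen. Both are restricted for 24 hours before screening and follow-up testing, and prescription depressants, including opioids, are restricted throughout.

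The Statistical Analyses entry in section 3.O covers only the transfer of data to SPSS. No criterion for when medication adjustment becomes necessary appears in the supplied text.

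**The concern.** Section 3.g describes the comparison the trial is built for: how adding TENS or sham TENS to TE augments the effect of TE alone. That is a total effect, and randomisation identifies it without adjusting for anything that happens afterwards.

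A covariate measured before randomisation can improve precision without changing that target. A covariate measured after randomisation, and possibly affected by treatment, cannot be relied on in the same way. If TENS changes pain and patients change their analgesic use in response, comparing arms at equal analgesic use is a different comparison. It removes part of what treatment did, and it also mixes in differences in severity between patients who reach the same drug use in different arms.

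The open condition adds a second difficulty. The decision to adjust can be taken after the data are seen, and section 3.h lists the person in charge of study analysis among the unblinded personnel.

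**Working it through.** **No plan figure to reproduce.** The documents give no effect size, standard deviation or correlation that bears on this point. The check is one of timing and logic, followed by an illustration with assumed values.

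**Step 1: timing.** Section 3.g.1 randomises patients after baseline testing and before the first physical therapy session. The daily log runs in each week of the intervention, so it is post-randomisation. The medication data collected at the baseline visit (3.j) are pre-randomisation.

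**Step 2: can treatment affect it?** Section 3.i.2 says that TENS may affect pain and makes the WOMAC pain subscale a secondary outcome. The TENS section cites clearance for pain associated with arthritis. A path from treatment through pain to analgesic use is therefore plausible on the plan's own terms.

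**Step 3: what adjustment would do.** Let A be treatment (0/1), U severity with variance 1, M on-study drug use and Y a pain score (lower is better). All parameters below are assumptions.

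*Model 1, drug use follows pain.* M = g(U − 0.5A) + noise (SD 0.8); Y = U − 0.5A − bM + noise. Here g is how strongly use responds to pain and b is how strongly the drug lowers the score.

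- Total effect = −0.5(1 − bg)
- Effect adjusted for M = −0.5(1 − r²), where r² = g²/(g² + 0.64)
- Ratio of adjusted to total = (1 − r²)/(1 − bg)

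For g = 0.3, r² = 0.09/0.73 = 0.123. For g = 0.6, r² = 0.36/1.00 = 0.36.

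| g | b = 0 | b = 0.2 | b = 0.5 | b = 0.8 |
|---|---|---|---|---|
| 0 | 1.00 | 1.00 | 1.00 | 1.00 |
| 0.3 | 0.88 | 0.93 | 1.03 | 1.15 |
| 0.6 | 0.64 | 0.73 | 0.91 | 1.23 |

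For example, at g = 0.6 and b = 0.8: 0.64/(1 − 0.48) = 1.23. A simulation of 400,000 patients agrees with the table to within 0.01. Adjustment shrinks the effect when r² exceeds bg and enlarges it when bg exceeds r².

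*Model 2, treatment shifts drug use directly.* M = −mA + gU + noise (SD 0.8), with the same Y.

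- Total effect = −0.5 + bm
- Adjusted effect = −0.5 + mg/(g² + 0.64)

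With m = 0.6, g = 0.4, b = 0: adjusted = −0.5 + 0.24/0.80 = −0.20 and total = −0.50, ratio 0.40 (simulated 0.39). With m = 0.6, g = 0, b = 0.5: adjusted = −0.50 and total = −0.5 + 0.30 = −0.20, ratio 2.50. These two cases are the extremes over m = 0.3 or 0.6, g = 0 or 0.4, and b = 0 or 0.5.

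**Step 4: reading the results.** Leaving M out recovers the total effect in every case. Including M leaves it unchanged when drug use responds to neither pain nor treatment. Otherwise the adjusted effect may be too small or too large, and nothing in the documents says which.

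**The case against.** The strongest reply is section 3.j. Patients are told to hold NSAID and acetaminophen use constant for 8 weeks, and opioids are restricted throughout. If they comply, on-study analgesic use hardly responds to treatment, g and m are near zero, and the ratio is close to 1.00. This stands as a limit on the concern. It does not remove it, because use is tracked rather than fixed. If use does come to differ between arms, the covariate clause allows adjustment in the setting where it can distort the comparison.

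A second reply is that the wording is conditional and the trial's focus is neuromuscular activation. Both are true. It would be wrong to say that adjustment is definitely planned, or that bias in the central activation ratio has been shown. But the clause is not confined to any outcome, and leaving the condition undefined is part of the problem.

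A reader might infer that adjustment would strip out part of a real TENS benefit, by a fraction r². That holds in Model 1 only when b = 0, meaning that analgesics do not affect the outcome. The 24-hour restriction before testing may reduce b, but the documents give no figure showing that it is zero. With a larger b the estimate is inflated instead.

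A reader might also take the Knee Injury History Form sentence as the same fault. It describes a screening form, so its medication data are most naturally pre-randomisation. It is ambiguous rather than wrong.

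Finally, the IRB protocol (Appendix A) is listed but its text was not available, and a fuller analysis section may exist there.

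**Conclusion.** The point stands in a limited form. The Medication Log clause permits discretionary adjustment for a variable measured after randomisation that treatment may affect. If the clause is used, the model no longer estimates the total effect of adding TENS to TE. The size and direction of the resulting bias cannot be predicted from the documents. The illustrative ratios, 0.64 to 1.23 in Model 1 and 0.40 to 2.50 in Model 2, rest wholly on assumed parameters. They show that either direction is possible and are not estimates for this trial.

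The concern is most direct for WOMAC pain and the pain VAS. It depends on imperfect compliance with the 3.j instructions and on the clause being used. It should be corrected before analysis because the correction is nearly free. It is not evidence that the trial's result will be wrong.

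**What to change.** Replace the covariate sentence under Medication Log with wording to this effect: only medication use recorded at baseline (current use and use in the previous 4 weeks, as collected under 3.j) may be a covariate in the main analysis; on-study medication use is summarised by arm for the period the log covers; any model that includes on-study use is labelled exploratory.

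Under Knee Injury History Form, clarify that the medication data meant as potential covariates are those collected at screening or baseline.

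State which weeks the log covers. The Duration of the Intervention text places it in the 4-week intervention, and the 4-week and 8-week follow-up form lists do not include it, while 3.j refers to tracking over 8 weeks. The by-arm summary should not promise data for weeks 5 to 8 unless they are collected.

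The cost is a few sentences of analysis wording. Baseline medication is already collected, and no new data or change in patient management is needed.

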### **VAS to assess tolerability of the intervention, satisfaction with the intervention, and likelihood to retain future appointments**

The VAS for tolerability of the intervention asks participants to make a vertical line on a 100mm solid line to indicate how tolerable they feel the intervention was during the past week. The VAS ranges from "Not at all Tolerable" on the left to "Extremely Tolerable" on the right. VAS scores closer to 100, or marks closer to the

rightward end, indicate a greater tolerability of the intervention. The VAS for satisfaction with the intervention asks participants to make a vertical line on a 100mm solid line to indicate how satisfied they are with the intervention during the past week. The VAS ranges from “Not at all Satisfied” on the left to “Extremely Satisfied” on the right. VAS scores closer to 100, or marks closer to the rightward end indicate a greater satisfaction of the intervention during the past week. The VAS for likelihood to retain future appointments asks participants to make a vertical line on a 100mm solid line to indicate how likely they are to retain their future appointment. The VAS ranges from “Not at all Likely” on the left to “Extremely Likely” on the right. VAS scores closer to 100, or marks closer to the rightward end, indicate a greater likelihood of retaining following appointments

#### *4-Week Follow Up Assessment*

Five questionnaires will be completed during the baseline assessment, which occurs within 7 days prior to the initiation of the intervention and includes 1) the Physical Activity Scale for the Elderly (PASE), 2) Self-Efficacy for Physical Activity (SEPA), 3) the Short Form 12 (SF-12), 4) the Charlson Morbidity Index, and 5) Visual Analog Scales (VAS) to determine the likelihood to continue current level of physical activity, current level of knee pain, and tolerability of walking.

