#### **3.i.2 Scope**

Outcome Measures are sectioned into Consent and Demographics, Self-reported outcomes, strength, function & gait and intervention outcomes. On baseline and follow-up testing performed in the Sports Medicine Research Laboratory the order of testing will always occur with Consent and Demographics, Self-reported outcomes, strength, and function & gait.

**Collecting of Recruitment, Inclusion and Retention Rates:** We will determine: 1) the number of patients recruited from various clinics and the frequency of recruitment using different recruitment modes (physician recommendation, mailings or other), 2) the percentage of patients that screen into the study compared to the number recruited, and 3) the percentage of patients retained at the 4- and 8-week post-tests (frequency of reasons for drop-out will be collected).

**Collecting Compliance, Adherence, and Tolerability of the Interventions Data:** We will determine the frequency and percentage of TE sessions that patients complete and record the usage of the TENS and sham TENS units. We will report adherence of all patients to the completion of 12 TE sessions over a 4-week period. A 10cm visual analog scale (VAS) will be used to quantify tolerability.

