**Quality of Life, Disease Related Self-Reported Disability, and Visual Analog Scales (VAS):** A paper version of the Short-Form (SF) 12 will be used to quantify the patients' quality of life. A paper version of the WOMAC score will be administered to each patient in a quiet room as previously performed by the PI. The total WOMAC score is useful as a measure of disability, yet important WOMAC subscale information regarding pain, stiffness and disability will also be analyzed separately. Although the focus of this study is TENS use to treat neuromuscular activation, we recognize that it may affect pain and will use the WOMAC pain subscale as a secondary outcome to assess pain. Three separate 10 cm VAS questionnaire will be used to assess the 1) current tolerability of walking, 2) the likelihood to continue the same level of physical activity, and 3) current pain level.

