### **3.n Data Collection and Study Forms**

#### **3.n.1 Source Documentation**

All data will be recorded on paper using black ink. All study forms will be printed prior to the beginning of the study and will be organized into participant binders which will contain all study documents necessary to collect each piece of data throughout the entirety of the study. All forms will be distributed to the study participant by either the Principal Investigator, Study Coordinator, or Research Assistant. The member of the study team will describe each of the questionnaires to the study participant, and will read allowed the instructions. The study participant will be allowed to ask any questions about the study questionnaires.

Each study participant will have one complete binder of study forms which consists of consent forms, case report forms, and all questionnaires to be completed by study participants. Each binder will contain packets of study forms, which correspond to the data needing to be collected during the following times throughout the course of the study: 1) initial screening, 2) baseline assessment 3) duration of the intervention, 4) 4-week follow up assessment and 5) 8-week follow up assessment. The study forms contained in each packet are individually described below.

All binders of study forms will be maintained in a locked file cabinet located within the Neuromuscular Research Laboratory. The Neuromuscular Research Laboratory is secured through UNC ID Card swipe access. The Principal Investigator, Study Coordinator, and Research Assistant are the only individuals who will have access to the file cabinet in which the participant binders are stored.

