### *8-Week Follow Up Assessment*

Six questionnaires will be completed during the baseline assessment, which occurs within 7 days prior to the initiation of the intervention and includes 1) the Physical Activity Scale for the Elderly (PASE), 2) Self-Efficacy for Physical Activity (SEPA), 3) the Short Form 12 (SF-12), 4) the Charlson Morbidity Index, 5) Visual Analog Scales (VAS) to determine the likelihood to continue current level of physical activity, current level of knee pain, and tolerability of walking, and 6) Knowledge of Group Assignment for Study Participants. One questionnaire will be completed by the member of the research team who will be conducting the 8-week follow-up which is the Knowledge of Group Assignment for Study Investigators.

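### The 4-week and 8-week form lists in section 3.n.1 omit WOMAC and carry baseline timing, although WOMAC pain is a secondary outcome

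*Combined protocol and SAP*

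**What the plan says.** Section 3.n.1 (Source Documentation) organises each participant's binder by time point: "Each binder will contain packets of study forms, which correspond to the data needing to be collected during the following times". The five times are screening, baseline, the intervention period, 4 weeks and 8 weeks. The section adds that the forms in each packet are described in the text that follows, and that all forms are printed before the study starts.

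- **Initial Screening:** "Three study forms will be completed during the initial screening session": the consent form, the Knee Injury History Form and WOMAC.
- **4-Week Follow Up Assessment:** "Five questionnaires will be completed during the baseline assessment, which occurs within 7 days prior to the initiation of the intervention". The five are PASE, SEPA, SF-12, Charlson and the VAS set.
- **8-Week Follow Up Assessment:** "Six questionnaires will be completed during the baseline assessment, which occurs within 7 days prior to the initiation of the intervention". These are the same five, and the list ends "and tolerability of walking, and 6) Knowledge of Group Assignment for Study Participants". An investigator blinding form is added separately.

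Section 3.i.2 describes the outcomes. For baseline and follow-up testing in the laboratory, "the order of testing will always occur with Consent and Demographics, Self-reported outcomes" come first, followed by strength, then function and gait. The paragraph on quality of life and self-reported disability says the investigators "will use the WOMAC pain subscale as a secondary outcome to assess pain". It treats the WOMAC total as a measure of disability and adds that "important WOMAC subscale information regarding pain, stiffness and disability will also be analyzed separately".

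**The concern.** The two sections give different instructions. Section 3.i.2 makes WOMAC a treatment outcome, which requires measurement after treatment. Section 3.n.1, which tells staff what to put in front of the participant at each visit, provides WOMAC only at screening, before randomization. An outcome measured only then cannot show a treatment effect.

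The lead sentence in both follow-up sections is the one used correctly under Baseline Assessment, which suggests how the omission arose. The baseline list can leave WOMAC out because it has just been completed at screening. Once the list was carried forward, the omission reached visits where no screening form can stand in.

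Nothing in section 3.n.2 would reliably catch the error. The completeness check there reviews the forms that a participant fills in, so it would not flag a form that was never in the packet. A missed self-report cannot be recovered after the visit.

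**Working it through.** There is no plan figure to reproduce. The check is an item-by-item comparison of the packet lists in section 3.n.1.

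| Packet | Forms stated | Forms named | WOMAC | Knee-pain VAS | SF-12 |
|---|---|---|---|---|---|
| Screening | 3 | 3 | yes | no | no |
| Baseline | 5 | 5 | no | yes | yes |
| Intervention period | none given | medication log, weekly VAS | no | no | no |
| 4-week | 5 | 5 | no | yes | yes |
| 8-week (participant) | 6 | 6 | no | yes | yes |

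1. **WOMAC coverage.** It is in 1 of 5 packets and 0 of 2 follow-up packets. The stated counts equal the named items, so WOMAC is not an uncounted extra. The form-by-form descriptions after each follow-up list also leave it out.
2. **Timing.** The 4-week sentence matches the baseline sentence, and the 8-week sentence changes only the count. Both place a follow-up visit in the 7 days before the intervention. Section 3.n.1 therefore gives no usable window for either follow-up.
3. **Requirement.** Section 3.i.1 sets laboratory testing at baseline, 4 weeks and 8 weeks. Section 3.i.2 includes self-reported outcomes in follow-up testing and names WOMAC pain as a secondary outcome.
4. **What cannot be computed.** The subscales described in section 3.n.1 are pain (5 items, 0–20), stiffness (2 items, 0–8) and function (17 items, 0–68). Together they have 5 + 2 + 17 = 24 items and a total range of 0 to 20 + 8 + 68 = 96. With no follow-up form, 0 of these 4 change scores are available.
5. **What survives.** The knee-pain VAS and SF-12 are in 3 of 3 assessment lists, and the SF-12 covers bodily pain and physical functioning. The performance tests in section 3.i.2 do not depend on these lists. No other listed follow-up form measures stiffness or knee-OA-specific self-reported function.
6. **Forms at stake.** With the target of 90 participants and two follow-ups, the ceiling is 90 × 2 = 180. The documents give no dropout rate. Assuming 20% loss at both visits, 90 × 0.80 = 72 and 72 × 2 = 144.

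**The case against.** The strongest reply is that the data loss is inferred. Section 3.i.1 refers the schedule of evaluations to a timeline in Appendix A, and Appendix E is titled for study visits and evaluations. Neither was available for this review, and either may schedule WOMAC at follow-up. Section 3.n.1 also says the binder holds all the questionnaires participants will complete, so a scheduled WOMAC might be included anyway. The packet lists are not a full inventory, since no case report form for activation, gait or performance testing is named in them. Section 3.i.2 does not state the WOMAC visits, and no passage defines a WOMAC change score.

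Much of this stands as a limit on the claim. The text does not prove that follow-up WOMAC was never planned. The form counts are only a scale, and the 20% loss is an assumption.

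It does not remove the conflict. The general statement about all questionnaires does not say which form belongs to which visit. The follow-up sections do, with counts that match their items. Missing case report forms for laboratory measures do not explain why a questionnaire is absent from an itemised list of questionnaires. A correct appendix would leave staff with two conflicting instructions, and the timing sentence would still be impossible. Measurement at follow-up is the natural reading of a secondary outcome in a trial tested at 4 and 8 weeks.

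**Conclusion.** The concern holds. As written, the follow-up lists in section 3.n.1 contradict section 3.i.2 and give a time window that cannot apply to the visits they describe. If binders are built from them, the named secondary pain outcome, the knee-OA-specific self-reported function score, stiffness and the WOMAC total would all lack post-treatment values in every arm.

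Confidence is high that the text is inconsistent. The predicted loss depends on staff following section 3.n.1 rather than an appendix not seen here. The neuromuscular activation outcome and eligibility screening by WOMAC are not affected, and some follow-up data on pain and function would remain. This should be fixed: a secondary outcome is at risk and the correction is simple.

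**What to change.** 1. Check the Appendix A timeline and Appendix E for the intended WOMAC visits, and state which document governs binder assembly.
2. In the 4-week section, open with: *Six questionnaires will be completed at the 4-week follow-up assessment (Follow-up 1)*, and add WOMAC to the five listed.
3. In the 8-week section, open with: *Seven questionnaires will be completed at the 8-week follow-up assessment (Follow-up 2)*, and add WOMAC to the six listed.
4. Delete the baseline timing from both sections and give each follow-up its own visit window, consistent with the schedule.
5. State that the screening WOMAC is the pre-treatment value for change scores, since the baseline list does not repeat it.
6. Align both lists with section 3.i.2.

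The cost is a text edit to two lists and one 24-item paper form, already in use at screening, at two visits already scheduled. No new visit or staff is needed.
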